3.6 Randomization Method and Masking

Consenting women will be assigned to pravastatin or placebo in a 1:1 ratio according to a randomization sequence prepared and maintained centrally by the Biostatistical Coordinating Center (BCC). The two study medication arms of the study (pravastatin or placebo) are double masked; neither the patient nor the clinical staff will be aware of the treatment assignment.

The simple urn method will be used to generate the randomization sequences because it provides a high probability of balance in treatment assignments, it is unpredictable, and it allows an explicit randomization analysis to be conducted with relative ease.¹⁰³ Randomization will be stratified by clinical site to assure balance between the two treatment groups with respect to anticipated differences among the clinic population and possible differences in patient management.

4 Study Procedures

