- Rhabdomyolysis: muscle symptoms (myalgia or weakness) plus CK $\geq 10x$ ULN or 10x baseline CK plus an elevation in serum creatinine (usually with brown urine and myoglobinuria) or need for medical interventions such as hospitalization and intravenous hydration.¹⁰⁴⁻¹⁰⁹
- Serious liver injury defined as persistent AST or ALT of 3 x ULN or increased AST or ALT levels with clinical symptoms and hyperbilirubinemia or jaundice, in the absence of severe preeclampsia or other hepatic disease

Severe Adverse Events of Special Interest will be defined as maternal myositis, myopathy, rhabdomyolysis, or serious liver injury. Patients will be advised throughout the study to report promptly unexplained muscle pain, tenderness or weakness, particularly if accompanied by malaise or fever. If myositis, myopathy, rhabdomyolysis, or serious liver injury occurs, the study drug (regardless of actual treatment assignment) will be discontinued permanently. If a patient develops myalgia or muscle weakness (documented on physical exam) with CK elevation $<3x$ ULN (or baseline CK), then the following will take place, 1) study drug will be stopped temporarily, 2) a workup will be done to ensure the patient does not have any of the other more serious muscle related serious adverse events, and 3) risk and precipitating factors will be evaluated. The patient will be monitored until complete resolution of symptoms and the CK values are back to normal (if applicable). The CK values will be checked weekly if above the ULN or baseline CK. Upon resolution, the patient will be re-challenged with pravastatin to be used every day or every other day.

Any woman who withdraws from taking study medication for any reason, including discontinuation for side effects, will be encouraged to continue study visits as planned, including the postpartum contact and follow-up of the child through 5 years of age.

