- c) Impaired liver function (elevated transaminases ≥ 70 U/L, or severe persistent right upper quadrant or epigastric pain unresponsive to medication)
- d) Pulmonary edema diagnosed clinically by exam or chest x-ray
- e) New-onset and persistent (non-responsive to supportive treatment) cerebral or visual symptoms.

3. HELLP [hemolysis, elevated liver enzymes and low platelet count] syndrome defined as the occurrence of all of the following (not accounted for by alternative diagnoses):

- a) Hemolysis: evidenced by (1) serum total bilirubin ≥ 1.2 mg/dL (20 μ mol/L), (2) serum lactate dehydrogenase (LDH) ≥ 600 IU/L, or (3) hemolysis on peripheral smear
- b) Thrombocytopenia (platelet count < 100,000 / microliter)
- c) Serum aspartate aminotransferase (AST) or alanine transaminase (ALT) ≥ 70 IU/L

4. Atypical HELLP defined as the occurrence of 2 of the 3 following (not accounted for by alternative diagnoses)

- a) Hemolysis: evidenced by (1) serum total bilirubin ≥ 1.2 mg/dL (20 μ mol/L), (2) serum lactate dehydrogenase (LDH) ≥ 600 IU/L, or (3) hemolysis on peripheral smear
- b) Thrombocytopenia (platelet count < 100,000 / microliter)
- c) Serum aspartate aminotransferase (AST) or alanine transaminase (ALT) ≥ 70 IU/L

5. Eclampsia defined as an occurrence of a seizure without any known cause

6. Competing outcomes also qualify as the primary outcome

- a) Maternal death before delivery
- b) Fetal loss less than 20 weeks, 0 days

All charts of women who have any elevated BP $\geq 140/90$ mmHg or a diagnosis of proteinuria, will be centrally reviewed by teams of three Protocol Subcommittee members (three investigators/nurse coordinators) blinded to assignment to ensure integrity of the primary and key secondary outcomes.

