5.4.3 Trial Stopping Rules

For the primary outcome, the group sequential method of Lan and DeMets will be used to characterize the rate at which the type I error is spent.¹¹² This method is flexible with regard to the timing of the interim analyses. Asymmetric stopping boundaries will be used. The upper boundary which describes the stopping rule for benefit will be based on 1-sided type I error of .025 and the Lan-DeMets generalization of the O'Brien-Fleming boundary. The lower boundary will be based on a less stringent stopping rule: 1-sided type I error of .05 and the Lan-DeMets generalization of the Pocock type boundary.

It is also planned to calculate conditional power given the observed data to date, and conditional on the future data showing the originally assumed design effect. If this conditional power is low (under 10 percent) the DSMC may consider termination for futility if the accrual rate is slow, with confidence that the Type II error is not greatly inflated.¹¹³

Specific stopping rules for the trial will be established for monitoring maternal, neonatal and child events relevant to pravastatin risk. For the maternal stopping rule, an occurrence of one of the following events will qualify:

- Serious Adverse Event of Special Interest (serious AESI; myositis, myopathy, rhabdomyolysis or serious liver injury as defined in Section 4.5).
- Non-serious AESI (myalgia or muscle weakness as defined in Section 4.5) that required repeat discontinuation of study medication (initial discontinuation, rechallenge, discontinuation again)

For the neonatal stopping rule the following event will qualify:

- Failed newborn ABR/OAE test

The BCC will continuously monitor these maternal and neonatal events and if there is an excess of women in the pravastatin group who have experienced one or more of the events such that the one sided nominal p-value of a Fisher's exact test is less than 0.05 or such that the lower 90% confidence bound of the relative risk exceeds 1.0 for larger sample sizes of 50 or more, will request that the DSMC review the

data immediately and make a determination on stopping or pausing the trial, or modifying the dose. Likewise if there is an excess of neonates who have failed their hearing tests, the same stopping criteria will apply.

For the child stopping rule, the following events will qualify:

- Cognitive or Motor Scale Score < 70 (2.5th percentile) from the Bayley Certified Scales of Infant Development 4 at 24 months age

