6.2 Sample Size and Power

In all of the older studies, except the High Risk Aspirin study, aspirin was not being used routinely. In the High Risk Aspirin trial, the dose was lower than is generally used today and was started later in gestation. Therefore, for the purposes of sample size estimation, it is conservatively assumed that all women will be receiving low dose aspirin, and that the rate of preeclampsia (primary outcome) in the placebo group is 20%. It is estimated that a sample size of 1,550 women is required to demonstrate at least a 30% reduction in preeclampsia with the use of pravastatin (from 20% to 14%), with a power of 85%, and type I error of 5% 2-sided. The sample size is adjusted for a drop-out rate of 5% (i.e. that 5% of the women on pravastatin discontinued their study drug and had the same primary outcome rate as the placebo group) and for the interim 'looks' at 50% and 75% information.

Table 5. Sample Sizes for Different, Levels of Power and Effect Sizes

Reduction in Primary Outcome Rate	Power %	Estimated Sample Size
25%	80	2000
	85	2280
	90	2660
30%	80	1360
	85	1550
	90	1810
35%	80	980
	85	1120
	90	1290

Trials evaluating cardiovascular disease event rates have reported that the combination of pravastatin and aspirin consistently has greater efficacy than pravastatin or aspirin alone indicating at least an additive and possibly a synergistic effect.¹¹⁹ Therefore, there is minimal concern that concomitant aspirin use would reduce the effect size.

Preterm birth < 37 weeks of gestation is considered to be the major secondary outcome. With a sample size of 1550, there is more than 80% power to detect an effect as small a 20% reduction in preterm birth.

The sample size for this study is also sufficient to detect with at least 80% power a 40% reduction in preterm delivery < 34 weeks and a 30% reduction in NICU/special care admission.

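### A liver event in a newly hypertensive woman can be scored as preeclampsia and, by the same laboratory value, dropped from the maternal safety count

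*Combined protocol and SAP*

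**What the plan says.** Section 4.5 defines serious liver injury in two ways: a persistent AST or ALT of three times the upper limit of normal (ULN), or raised AST or ALT with symptoms and hyperbilirubinemia or jaundice. It then adds the condition "in the absence of severe preeclampsia or other hepatic disease". We read that condition as applying to both.

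Section 4.6.1 uses liver values in the primary outcome in several places:

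- Item 1(b)(iv), previously normotensive women: mild hypertension from 20 weeks with transaminases of 70 U/L or more. No clause on alternative diagnoses is attached.
- Item 2, chronic hypertension: transaminases of 70 U/L or more, subject to such a clause.
- Item 4: "Atypical HELLP defined as the occurrence of 2 of the 3 following (not accounted for by alternative diagnoses"). The three criteria are hemolysis, platelets below 100,000 per microliter, and AST or ALT of 70 IU/L or more. Total bilirubin of 1.2 mg/dL or more is enough for hemolysis.

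Section 4.6.2, item 4, names impaired liver function among the features that make preeclampsia severe.

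Section 5.4.3 takes as a maternal stopping-rule event a "Serious Adverse Event of Special Interest (serious AESI; myositis, myopathy, rhabdomyolysis or serious liver injury as defined in Section 4.5"), together with repeat discontinuation for myalgia or weakness.

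Masked central review (end of Section 4.6.1) covers charts with elevated blood pressure or proteinuria.

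**The concern.** Liver injury is one of the four serious events chosen for the maternal stopping rule, so its definition should not depend on a diagnosis that the same laboratory result can create. Here it can. A transaminase value that completes the definition of preeclampsia in a hypertensive woman also makes that preeclampsia severe, and severe preeclampsia removes her from the liver-injury count.

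Two things are at stake. The count that prompts immediate DSMC review may be too low on pravastatin. The primary comparison may also gain pravastatin events that are not preeclampsia, which pulls the estimate toward no effect.

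**Working it through.** **1. Following one case through the text.** Take a previously normotensive woman with blood pressure of 140/90 on two occasions, a persistent ALT above three times ULN, and no proteinuria. Suppose the drug caused the liver change.

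- Section 4.6.1, item 1(b)(iv): the primary outcome is met. Nothing in the item lets a reviewer set it aside because of another cause.
- Section 4.6.2, item 4: impaired liver function makes it preeclampsia with severe features.
- Section 4.5: severe preeclampsia is present, so she does not have serious liver injury.
- Section 5.4.3: she is not a liver event for the maternal rule.

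The one inference is that severe preeclampsia in Section 4.5 means preeclampsia with severe features in Section 4.6.2.

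The thresholds overlap: 3 × ULN is at least 70 whenever ULN is at least 70/3 = 23.3 U/L. An assumed ULN of 30 to 45 gives 90 to 135.

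**2. Atypical HELLP.** Bilirubin of 1.2 mg/dL with ALT of 70 IU/L meets two of the three criteria with normal platelets and blood pressure. With symptoms, such values can also fit the second form of serious liver injury. Section 4.6.1 asks that alternative diagnoses be excluded first, and Section 4.5 asks that severe preeclampsia or other hepatic disease be excluded first. Neither says which is settled first. A woman with no elevated blood pressure and no proteinuria is outside the stated trigger for central review.

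**3. The plan's design figure.** Inputs from Section 6.2: 20% against 14%, "with a power of 85%, and type I error of 5% 2-sided", and dilution because "5% of the women on pravastatin discontinued their study drug and had the same primary outcome rate as the placebo group". Section 3.6 gives the 1:1 allocation.

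- Diluted pravastatin rate: 0.95 × 14% + 0.05 × 20% = 14.3%.
- Pooled two-proportion formula, 20% against 14.3%: 784 per arm, 1,568 in total, against the stated 1,550. The design is reproduced to about 1%.
- Power at 775 per arm: 84.6% without interim looks.

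**4. The Fisher criterion.** One-sided exact p, liver events only, none on placebo:

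| Per arm | 4 v 0 | 5 v 0 |
|---|---|---|
| 25 | 0.055 | 0.025 |
| 155 | 0.061 | 0.030 |
| 775 | 0.062 | 0.031 |

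At the threshold, one relabelled case removes the trigger. This is the sharpest case: the rule also counts muscle events, and for larger samples it uses a lower 90% bound on the relative risk.

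**5. An undercount over an assumed range.** The documents give no rate for this event. Take true rates of 1.0%, 1.4% and 1.8% on pravastatin, none on placebo, 775 per arm. The chance of five or more counted events is 89%, 98% and 99.8% if all are counted, and 35%, 63% and 83% if half are relabelled. The last two rates are the AST and ALT figures in Section 2.5.4. They come from higher doses and carry no bilirubin condition, so they are generous here.

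**6. The primary comparison over an assumed range.** If a share m of otherwise event-free pravastatin women is scored as preeclampsia, the rate is 0.143 + m × 0.857.

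| m | Pravastatin rate | Power at 775 per arm |
|---|---|---|
| 0 | 14.3% | 84.6% |
| 0.25% | 14.5% | 82% |
| 0.5% | 14.7% | 78% |
| 1.0% | 15.2% | 71% |

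The 1.0% row means 775 × 0.857 × 0.01 = 6.6 misclassified women, more than the documents give reason to expect.

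**The case against.** Four arguments favor the plan as written.

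- **Safeguards.** The masked medical monitor reviews classification and relatedness (Section 5.3). The DSMC receives adverse events and outcomes by coded group (Section 5.4.1) and holds safety reviews after 50 and 310 deliveries (Section 5.4.2). Three masked reviewers read every hypertensive chart. A reader might infer that the stopping rule is blind to liver harm. It is not: such a case remains reportable, and what can be lost is its place in the formal count.
- **Scope.** A reader might infer that liver injury and the primary outcome exclude each other, so that 14% to 20% of women fall outside the liver count. The text does not support this. Section 4.5 excludes severe preeclampsia, so a woman with proteinuric preeclampsia without severe features, or with a fetal loss, can still be counted.
- **Atypical HELLP.** A reader might infer that a normotensive woman with raised bilirubin and transaminases is certain to be lost. That is also too strong. Drug injury is an alternative diagnosis under item 4, and neither Section 4.5 nor the severe-feature list names HELLP. The text is ambiguous here.
- **Specificity.** Leaving disease-related events out keeps the safety count specific. Assume HELLP in 1% of placebo women (about 8 of 775) and 30% less on pravastatin (about 5). Five true drug injuries then give 10 against 8, p = 0.41, where 5 against 0 gives 0.031.

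All four stand as limits. None removes the route through item 1(b)(iv), which has no alternative-diagnosis clause. The specificity argument decides the form of the remedy: an unattributed count should not replace the current event.

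**Conclusion.** The concern holds in a limited form. For newly hypertensive women, stated rules can turn a drug-related liver event into a primary outcome and remove it from the maternal stopping-rule count. For atypical HELLP the two definitions are circular, and the outcome depends on whoever classifies the case.

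The effect is a possible undercount of liver harm and a bias against pravastatin on efficacy. Relabelling drug injuries in this way cannot create a false benefit. The size is unknown and probably small. Section 2.5.4 reports marked aminotransferase elevations below 1.2% and similar to placebo in the long-term trials, with liver abnormalities usually free of symptoms and cholestasis, and the pilot had no liver injury. The rates in steps 5 and 6 are assumptions that show sensitivity and are not forecasts. This is a cheap improvement and not a flaw that threatens the trial.

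**What to change.** 1. Reconcile the liver-related definitions in Sections 4.5, 4.6.1 and 5.4.3: state the order of precedence and who classifies a case that meets both sets of values, including one without elevated blood pressure or proteinuria. Which definition prevails is for the investigators. Section 4.5 also ties permanent discontinuation of study drug to the same term, so the wording must agree there too.
2. Keep the existing stopping-rule event. Add to the DSMC report a parallel count by arm of every woman who meets the laboratory liver-injury thresholds, whatever the attribution, split by masked attribution.
3. Add one sensitivity analysis of the primary outcome that leaves out events resting only on transaminases, with or without bilirubin.

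The cost is some wording, one table and one analysis, with no change to visits, treatment or sample size. HELLP will add background in both arms, so the parallel count should supplement the rule and not replace it. The visit schedule lists AST/ALT only at screening, so the table will rest mainly on values obtained in clinical care.

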4.6 Study Outcome Measures and Ascertainment

4.6.1 Primary Outcome

The primary outcome of the study is a composite of fetal loss, maternal death, and preeclampsia diagnosed prior to 48 hours postpartum as follows:

1. In previously normotensive women, preeclampsia is diagnosed based on
 - a) Severe hypertension (systolic blood pressure ≥ 160 mmHg or diastolic blood pressure ≥ 110 mmHg) at ≥ 20 weeks in gestation on two occasions with measurements taken at least 4 hours apart, or 1 occasion with subsequent anti-hypertensive therapy, or
 - b) Mild hypertension (systolic blood pressure ≥ 140 mmHg or diastolic blood pressure ≥ 90 mmHg) at ≥ 20 weeks in gestation on two occasions with measurements taken at least 4 hours apart, with any of the following:
 - i. New-onset proteinuria ≥ 300 mg in a 24-hour period, protein to creatinine ratio ≥ 0.3 , or 1+ protein on maternal urine dipstick (only if 24-hour urine collection or protein to

creatinine ratio is not possible) or a doubling in protein in women with baseline proteinuria

- ii. Thrombocytopenia (platelet count <100,000 per microliter)
- iii. Progressive renal insufficiency (serum creatinine >1.1 mg/dl or doubling of the serum creatinine in women with abnormal baseline values (>1.1 mg/dl) and in the absence of other renal disease)
- iv. Impaired liver function (elevated transaminases ≥ 70 U/L, or severe persistent right upper quadrant or epigastric pain unresponsive to medication)
- v. Pulmonary edema diagnosed clinically by exam or chest x-ray
- vi. New-onset and persistent (non-responsive to supportive treatment) cerebral or visual symptoms.

2. In women with baseline chronic hypertension, preeclampsia is diagnosed based on any of the following (not accounted for by alternative diagnoses):

- a) Severe hypertension (systolic blood pressure ≥ 160 mmHg or diastolic blood pressure ≥ 110 mmHg) ≥ 20 weeks in gestation on two occasions with measurements taken at least 4 hours apart, or 1 occasion with subsequent anti-hypertensive therapy, or an escalation of antihypertensive medications to control blood pressure
- b) New onset of proteinuria or a doubling in protein in women with baseline proteinuria
- a) Thrombocytopenia (platelet count <100,000 per microliter)
- b) Progressive renal insufficiency (serum creatinine >1.1 mg/dl or doubling of the serum creatinine in the absence of other renal disease)
- c) Impaired liver function (elevated transaminases ≥ 70 U/L, or severe persistent right upper quadrant or epigastric pain unresponsive to medication)
- d) Pulmonary edema diagnosed clinically by exam or chest x-ray
- e) New-onset and persistent (non-responsive to supportive treatment) cerebral or visual symptoms.

3. HELLP [hemolysis, elevated liver enzymes and low platelet count] syndrome defined as the occurrence of all of the following (not accounted for by alternative diagnoses):

- a) Hemolysis: evidenced by (1) serum total bilirubin ≥ 1.2 mg/dL (20 μ mol/L), (2) serum lactate dehydrogenase (LDH) ≥ 600 IU/L, or (3) hemolysis on peripheral smear
- b) Thrombocytopenia (platelet count < 100,000 / microliter)
- c) Serum aspartate aminotransferase (AST) or alanine transaminase (ALT) ≥ 70 IU/L

4. Atypical HELLP defined as the occurrence of 2 of the 3 following (not accounted for by alternative diagnoses)

- a) Hemolysis: evidenced by (1) serum total bilirubin ≥ 1.2 mg/dL (20 μ mol/L), (2) serum lactate dehydrogenase (LDH) ≥ 600 IU/L, or (3) hemolysis on peripheral smear
- b) Thrombocytopenia (platelet count < 100,000 / microliter)
- c) Serum aspartate aminotransferase (AST) or alanine transaminase (ALT) ≥ 70 IU/L

5. Eclampsia defined as an occurrence of a seizure without any known cause

6. Competing outcomes also qualify as the primary outcome

- a) Maternal death before delivery
- b) Fetal loss less than 20 weeks, 0 days

All charts of women who have any elevated BP $\geq 140/90$ mmHg or a diagnosis of proteinuria, will be centrally reviewed by teams of three Protocol Subcommittee members (three investigators/nurse coordinators) blinded to assignment to ensure integrity of the primary and key secondary outcomes.

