3.4.3 Exclusion Criteria

1. Monoamniotic gestation because of the risk of fetal demise
2. Known chromosomal, genetic or major malformations
3. Fetal demise or planned termination of pregnancy. Selective reduction by 13 weeks 6 days gestation, from triplets to twins or twins to singleton is not an exclusion.
4. Contraindications for statin therapy:
 - a. Hypersensitivity to pravastatin or any component of the product
 - b. Active liver disease: acute hepatitis or chronic active hepatitis
5. Statin use in current pregnancy
6. Patients with any of the following medical conditions:
 - a. Uncontrolled hypothyroidism with a TSH level above 10 mIU/L, because of increased risk of myopathy
 - b. HIV positive, because of increased risk of myopathy with use of protease inhibitors
 - c. Chronic renal disease with baseline serum creatinine ≥ 1.5 mg/dL, because of association with adverse pregnancy outcomes
7. Current use of concomitant medication with potential for drug interaction with statins (i.e., cyclosporine, fibrates, niacin, erythromycin). Patients will not be excluded if the drug is discontinued (at least one week) prior to randomization.
8. Participating in another intervention study that influences the primary outcome in this study
9. Plan to deliver in a non-network site
10. Participation in this trial in a previous pregnancy. Patients who were screened in a previous pregnancy, but not randomized, do not have to be excluded.

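### Section 4.6.1 does not hold women with chronic hypertension to item 1's 20-week limit and thresholds, and its escalation clause can be read two ways

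*Combined protocol and SAP*

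**What the plan says.** Section 4.6.1 defines preeclampsia separately for two groups of women.

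- **Item 1, previously normotensive women.** Both routes, severe hypertension (1a) and milder hypertension with an added feature (1b), require the hypertension at 20 weeks or later. Proteinuria has numerical thresholds. The creatinine doubling rule is tied to women whose baseline is abnormal (above 1.1 mg/dL).
- **Item 2, women with baseline chronic hypertension.** Any one listed finding is enough, provided an alternative diagnosis does not account for it. Item 2a is severe hypertension at 20 weeks or later, on two occasions, or on one occasion followed by antihypertensive therapy, "or an escalation of antihypertensive medications to control blood pressure". Item 2b is "New onset of proteinuria or a doubling in protein in women with baseline proteinuria". The renal criterion is "Progressive renal insufficiency (serum creatinine >1.1 mg/dl or doubling of the serum creatinine in the absence of other renal disease". Platelet, liver, pulmonary edema and cerebral or visual criteria follow.
- **Items 3 to 5.** HELLP, atypical HELLP and eclampsia apply to every woman.

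The opening sentence of 4.6.1 sets a latest time for the diagnosis (48 hours postpartum) but no earliest time. Section 3.4.1 sets randomization between 12 weeks 0 days and 16 weeks 6 days. Section 3.4.3 excludes "Chronic renal disease with baseline serum creatinine" of 1.5 mg/dL or more. Charts with blood pressure of 140/90 or above, or with proteinuria, go to central review masked to assignment.

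**The concern.** The primary endpoint should mean the same thing in every woman and to every adjudicator. As item 2 is written, a finding at 14 or 18 weeks can be scored as preeclampsia in a woman with chronic hypertension, although section 2.1 describes a syndrome of the second half of pregnancy. A baseline creatinine between 1.1 and 1.5 mg/dL can meet the letter of the renal criterion. Two adjudicators could also score the same chart differently when antihypertensive drugs were increased without a severe-range reading.

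Events admitted this way that pravastatin affects less than true preeclampsia pull the relative risk toward 1 and can cost power. They also raise the placebo rate. Section 5.4.2 has that rate examined after the first 310 women randomized have delivered, to decide whether the sample size needs revision. A rate raised by such events would look reassuring while the effect to be detected was shrinking.

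**Working it through.** **1. The definitions side by side**

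| Feature | Item 1 (normotensive) | Item 2 (chronic hypertension) | Items 3–5 (all women) |
|---|---|---|---|
| 20-week limit | On the hypertension required by both routes | In 2a only | None |
| New proteinuria | Numerical thresholds | No threshold | – |
| Creatinine doubling | Tied to abnormal baseline (>1.1) | Baseline wording absent | – |
| Drug escalation | Not mentioned | At the end of 2a | – |

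From randomization to 20w0d is 8w0d for a woman entering at 12w0d and 3w1d for one entering at 16w6d. Item 2b and the criteria after it can be met during that time.

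The escalation clause follows a comma and an *or*. It can be a third way of meeting 2a, with no blood-pressure threshold. It can also be a second form of the treatment that follows one severe-range reading. The text does not decide between them.

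**2. The plan's own sample size**

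Inputs from section 6.2: "the rate of preeclampsia (primary outcome) in the placebo group is 20" per cent; "30% reduction in preeclampsia with the use of pravastatin (from 20% to 14" per cent; "with a power of 85%, and type I error of 5% 2-sided"; and "5% of the women on pravastatin discontinued their study drug and had the same primary outcome rate as the placebo group". Allocation is 1:1.

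- Pravastatin rate after discontinuation: 0.95 × 0.14 + 0.05 × 0.20 = 0.143.
- The pooled-variance formula for two proportions, 0.20 vs 0.143, gives 784 per arm, or 1,568 in total. This is 1.2% above the stated 1,550.
- Power = Φ{[√n·(p₁ − p₂) − 1.96·√(2p̄(1 − p̄))] / √(p₁(1 − p₁) + p₂(1 − p₂))}.
- With n = 775 per arm: (27.84 × 0.057 − 1.96 × 0.5331) / 0.5316 = 1.02, so power is 84.6%.
- The O'Brien-Fleming-type looks at 50% and 75% cost a factor of 1.019. With n = 775/1.019 = 760.5, power is 83.9%. This is the reference below.

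**3. Extra events that the drug does not affect (illustration)**

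The documents give neither the share *h* of women with chronic hypertension nor the proportion *e* of them who would gain an event only through escalation or a pre-20-week finding. Both are assumed here. Extra events are taken as independent of other events and unaffected by pravastatin. With x = h·e:

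- placebo rate: 1 − 0.80(1 − x)
- pravastatin rate: 1 − 0.857(1 − x) with discontinuation, or 1 − 0.86(1 − x) without it

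| h | e | x | Placebo | Pravastatin | RR (no discontinuation) | Power with looks | N for 85% |
|---|---|---|---|---|---|---|---|
| – | – | 0 | 20.0% | 14.3% | 0.700 | 84% | 1,598 |
| 10% | 5% | 0.5% | 20.4% | 14.7% | 0.707 | 83% | 1,645 |
| 20% | 10% | 2.0% | 21.6% | 16.0% | 0.728 | 80% | 1,789 |
| 40% | 30% | 12.0% | 29.6% | 24.6% | 0.822 | 60% | 2,871 |

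The last row is the far end of the assumed range. It needs extra events equal to more than half of the planned 20% rate.

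**4. Extra events that the drug does affect**

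Add x to the placebo rate and r·x to the 14% pravastatin rate, then apply the 5% discontinuation.

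| Drug effect on extra events | x = 2%: RR, power | x = 5%: RR, power |
|---|---|---|
| None (r = 1) | 0.727, 81% | 0.760, 76% |
| 15% reduction (r = 0.85) | 0.714, 85% | 0.730, 86% |
| 30% reduction (r = 0.70) | 0.700, 88% | 0.700, 92% |

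The relative risk moves toward 1 whenever the extra events respond less than true preeclampsia. Power falls below 84% only if they respond little: in this calculation, by less than about 12%.

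**The case against.** The strongest defense is that the intended meaning is clear enough. Item 2a is headed by severe hypertension at 20 weeks or later, and escalation sits inside it. Women with chronic hypertension may already be on treatment, so escalation is a natural counterpart of starting therapy after one severe reading. The item 2 header rules out findings that an alternative diagnosis accounts for. Routine up-titration for known hypertension, or a stable raised creatinine, could be set aside on that ground, and the renal criterion itself asks for progression and no other renal disease. Reviewers are masked. Item 6 treats fetal loss before 20 weeks as a competing outcome, which suggests that preeclampsia was not expected before then.

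Much of this stands. A reader might infer that escalation alone certainly counts; the documents support that only as one of two readings. A reader might also infer that these are events pravastatin cannot prevent. The protocol's background points the other way on blood pressure, in animal models (section 2.6.1) and in a 21-patient cohort (section 2.6.3), and step 4 shows that power could even rise.

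The defense does not close the gap. The header does not say whether chronic hypertension needing more drug is an alternative diagnosis. Section 4.5 leaves blood-pressure control to each institution, so escalation practice may vary by site. Masked reviewers apply the same text. Nothing in items 2b onward, or in items 3 to 5, states the limit that the defense takes as understood. Section 6.3 plans sensitivity analyses for loss to follow-up only. Chronic hypertension is a subgroup factor in 6.3.1, but that analysis depends on a significant interaction and does not separate the routes to an event.

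**Conclusion.** The inconsistency between items 1 and 2, and the missing limit in items 3 to 5, are plain on the page and should be corrected. The two readings of the escalation clause are a real ambiguity in the primary endpoint.

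The statistical consequence is conditional. With masking intact, any misclassification is non-differential, so the risk is a diluted effect and lost power, not a false benefit. On the two milder sets of assumptions the loss is about 1 point (84% to 83%) or 4 points (84% to 80%). Both assume that the drug has no effect on the extra events. A reader might take the 60% at the far end as a demonstrated loss; it is not, because the documents supply neither input, and the sign itself depends on how far pravastatin affects these events.

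This is a change that should be made because it concerns the primary outcome and costs little, not because the trial has been shown to be underpowered. Confidence is high on the text and low on the size.

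**What to change.** 1. State the 20-week limit once over all of item 2 and over items 3 to 5, or justify its absence. Item 6 (maternal death before delivery, fetal loss before 20 weeks) stays as it is.
2. Use item 1's proteinuria threshold and abnormal-baseline creatinine wording in item 2. Section 4.3 lists proteinuria but not serum creatinine among baseline items, so say where the baseline value comes from.
3. State which reading of the escalation clause adjudicators must apply, and whether chronic hypertension itself is an alternative diagnosis under the item 2 header.
4. Have the adjudication form record the qualifying criterion and its date.
5. Pre-specify a sensitivity analysis of the primary outcome that leaves out escalation-only and pre-20-week events. It removes events, not women. Once the limit is in force, it would bear mainly on escalation-only events and on any cases adjudicated under the present text.

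The cost is a wording amendment to the protocol and adjudication form, one small extra analysis, and some events that no longer count in the primary outcome.
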